#### Diagnostic procedures

The screen-positive men will undergo a multiparametric MRI using 3T equipment (Siemens Achieva) with 32-channel pelvic phased-array coil. T2-weighted, diffusion-weighted and dynamic contrast-enhanced imaging is employed in accordance with the European Society for Urogenital Radiology guideline. The findings will be classified according to the Prostate Imaging Reporting and Data System (PIRADS-2), which is a 5-point scale to combine the MRI findings and indicate the likelihood of a significant cancer (Osses 2017). A score of 4-5 indicates a PPV > 80% and also a score of 3 is regarded as a positive finding warranting biopsy. Standardisation of MRI procedures is ensured prior to the start of the trial, including slice orientation and thickness, and size of the matrix and field of view. Training sessions will be repeated annually throughout the conduct of the trial. Independent double reading for a random sample of the images is used for quality assurance, and to reduce false negative and false positive findings. Standardised and structured radiologists' reports will be obtained and prostate volume also recorded. Pseudoanonymised images are uploaded into the cloud-based trial database using the ECRF software tailored for the trial purposes.

The men with positive MRI will undergo targeted biopsy using fusion MRI-TRUS guidance (UroNav), with an additional core per each incremental 6 mm size of the lesion. The expected frequency of positive MRI is 60% of screen-positive men (4.7% of all screening participants), with a total of 521 men in the first round. To avoid missing cancers among high-risk men, those with PSA density (serum PSA divided by prostate volume) > 0.15  $\mu\text{g}/\text{ml}^2$  will be referred to systematic biopsy despite a negative MRI (Distler 2017). A random sample of those men with PSA  $\geq 3$  but (1) negative kallikrein panel and/or (2) negative MRI will also undergo systematic biopsy for assessment of diagnostic accuracy. A small number of men will not be eligible for MRI due to metal implants, and for them transrectal ultrasound (TRUS) will be used instead.

The prostate biopsies are evaluated by trained, experienced uropathologists under supervision of [name] in Helsinki and [name] in Tampere. Structured and standardised reports are used, with each core is evaluated separately and exact location recorded. Training and standardisation will be conducted

using virtual microscopy methods developed in Tampere (prof. [name]). The original pathology reports are retrieved from the system and incorporated into the trial database in an automated fashion.

The expected numbers of screen-detected cases in the first round is 290 (55% of men referred to MRI, or 2.6% of screening participants). Of the screen-detected cases, 75-80% are expected to be Gleason $\geq$ 7. Treatment of the detected cases is centralised at the Helsinki and Tampere university hospitals and follows the Finnish guidelines. Primary management options for localised cancer currently include active surveillance (according to EAU-ESTRO-SIOG guideline), radical prostatectomy (robot-assisted), external radiotherapy or brachytherapy. For locally advanced cases, combined modality with radiotherapy and endocrine treatment is treatment of choice. For metastatic cases (and localised cases with contraindications curative treatment), endocrine treatment (LHRH antagonists, antiandrogens) and watchful waiting are used. Any future developments in treatment policy is implemented in management of the cases in both arms of the trial. This is an ethical imperative and also satisfies the scientific requirement of similar treatment, given disease and patient characteristics, in both trial arms in order to avoid bias due to treatment.

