#### Screening protocol

Briefly, we will first screen men with total PSA and then use an array of four biochemical markers (4Kscore) among men with PSA>3 ng/ml to improve the diagnostic accuracy for clinically significant cancer (Gleason≥7), while reducing the number of biopsies and detection of Gleason<7 cancers. For diagnostic assessment of screen-positive men, we will use multiparametric MRI, aimed at reducing the detection of Gleason<7 prostate cancer by at least 50% by the combination of the screening test and diagnostics (Figure 1). Finally, the baseline serum PSA is used for determining the optimal screening interval, ranging 2-6 years.

[figure not shown]

Figure 1. Using three layers of risk stratification to identify men at highest risk.

The control arm will receive usual care, with no intervention (apart from collection of registry data for all men in both arms on the outcomes, including PSA testing, prostate cancer incidence and mortality, as well as questionnaire surveys for some subgroups).

Men in the screening arm will be invited to the first screen over a two-year period. We expect similar participation as in the previous Finnish prostate cancer screening trial (two thirds or 11,167 participants). This would mean that we would screen roughly 560 men per month (assuming 10 months of effective screening annually) (Figure 2).

In the baseline survey at entry to the study, screening participants are asked about their family history of prostate cancer, as well as established or suspected risk factors for prostate cancer (including BMI, alcohol consumption, physical activity and consumption of some foodstuffs). Information will be also collected on previous PSA tests and possible prior prostate biopsy from the hospital databases.

A 30 ml blood sample will be drawn at one of the service sites of the regional laboratory networks (HUSLab and FimLab) to an EDTA tube, with plasma and serum separated and frozen. Total and free PSA are analysed at HUSLab and FimLab with electrochemiluminescence immunoassay (ECLIA) for COBAS® 6000 analyser (Roche Diagnostics, Rotkreuz, Switzerland). Calibration is performed using the WHO standards (WHO 96/670 and 68/668 for total and free PSA).

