Based on the FinRSPC first round results, we expect that the proportion of men with  $PSA \geq 3$  is 13% overall (10% in men aged 53-57, 17% for ages 58-62 and 24% at ages 63-65), total expected  $N=1452$ . This would mean on average 75 kallikrein panel determinations per month.

Screening interval is based on the initial PSA: men with  $PSA \geq 3$  are re-invited after two years, those with  $PSA > 1.5$  after four years, and the men in the lowest risk group ( $PSA < 1.5$ ) after six years.

After serum PSA as the initial test, we will use a four-kallikrein panel (4Kscore) to identify men at an increased risk of a clinically relevant prostate cancer. The determinations will be performed by prof. [name] in his lab in Malmö, with samples shipped every two weeks. These men will be referred to MRI and only MRI-positive men will be biopsied (randomised to targeted biopsy alone versus targeted and systematic biopsy).

The men with the highest risk of Gleason 7+ prostate cancer based on the kallikrein panel (out of those with  $PSA > 3$ ) will be regarded as screen-positive and referred to diagnostic examination at Tampere or Helsinki University Hospital urology clinic. The expected frequency is 871 men in the first round (60% of men with  $PSA \geq 3$ , or 7.8% of all participants), on average 45 men referred to MRI each month. This is substantially lower than in the PSA-based ERSPC trial (where on average 13% of the participants were screening-positive and referred to biopsy in the first round).

[figure not shown]

Figure 2. A CONSORT diagram illustrating the trial protocol and the expected distribution of men by test results

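### The PSA-density threshold for biopsy after a negative MRI is printed in a unit 1,000 times too large, and the 55% cancer yield is attached to the wrong denominator

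*Combined protocol and SAP*

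**What the plan says.** All references are to section 4 (Methods) of the combined protocol and SAP unless stated.

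**Threshold.** Diagnostic procedures defines PSA density as serum PSA over prostate volume and uses it as a safeguard: "To avoid missing cancers among high-risk men, those with PSA density (serum PSA divided by prostate volume) > 0.15". The sentence continues with the unit and the action: "> 0.15 $\mu\text{g}/\text{ml}^2$ will be referred to systematic biopsy despite a negative MRI". Where PSA carries a unit elsewhere, it is ng/ml. Screening protocol applies the kallikrein panel in these terms: "then use an array of four biochemical markers (4Kscore) among men with PSA>3 ng/ml". The Background, under Optimising the screening algorithm, also gives PSA in ng/ml.

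**Expected numbers in round one.** Screening protocol gives the participants as "two thirds or 11,167 participants" and, for men sent on to MRI, states: "The expected frequency is 871 men in the first round". For MRI-positive men, Diagnostic procedures gives: "expected frequency of positive MRI is 60% of screen-positive men (4.7% of all screening participants), with a total of 521 men". The same section then expects 290 screen-detected cancers, described as 55% of those referred for MRI and as 2.6% of participants.

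**The concern.** The density threshold decides whether a man with a negative MRI has a systematic biopsy. A threshold of this kind tends to be copied into working procedures and electronic case report forms, so its unit should be usable as printed. Dividing ng/ml by ml gives ng/ml², and the printed unit is 1,000 times larger. Applied literally, the safeguard would select nobody, which defeats its stated purpose.

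The 55% looked wrong because the sentence does not agree with itself. If 55% of the men referred for MRI had cancer, neither the count of 290 nor the 2.6% of participants could be right. At stake is a correctly labelled expected yield: the chance of cancer per man referred for MRI and the chance per MRI-positive man differ considerably and should not be interchangeable.

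**Working it through.** **Inputs.** PSA cut-off 3 ng/ml, 11,167 participants, 13% with PSA at or above 3 (1,452 men), and 871 men referred for MRI (60% of 1,452), all from Screening protocol. From Diagnostic procedures: 521 MRI-positive men, 290 expected cancers, and the density threshold of 0.15 µg/ml².

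**Step 1. Reproduce the plan's cascade.**
- PSA at or above 3: 0.13 × 11,167 = 1,451.7 (printed 1,452).
- Referred for MRI: 0.60 × 1,452 = 871.2 (printed 871); 871/11,167 = 7.8% (as printed).
- MRI-positive: 0.60 × 871 = 522.6 (printed 521, within two men); 521/11,167 = 4.7% (as printed).
- Cancers: 290/11,167 = 2.6% (as printed).

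The counts and these percentages agree with one another.

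**Step 2. Test the 55%.**

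| Denominator | 290 as a percentage | Cancers implied by 55% | Implied share of 11,167 |
|---|---|---|---|
| 871 referred for MRI (as labelled) | 290/871 = 33.3% | 0.55 × 871 = 479 | 4.3% |
| 521 MRI-positive | 290/521 = 55.7% | 0.55 × 521 = 287 | 2.6% |

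On the labelled denominator the figure fails by a margin that rounding cannot explain. On the MRI-positive men it fits to within a few cases.

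**Step 3. Convert the threshold.** Since 1 µg = 1,000 ng, 0.15 µg/ml² = 150 ng/ml². A man exceeds the threshold when volume < PSA / threshold. At PSA 3 ng/ml:
- as printed: 3/150 = 0.02 ml;
- in ng/ml²: 3/0.15 = 20 ml.

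The documents give no prostate volumes. Assuming 20 to 100 ml, the PSA needed to exceed the threshold (threshold × volume) is:
- as printed: 150 × 20 = 3,000 to 150 × 100 = 15,000 ng/ml;
- in ng/ml²: 0.15 × 20 = 3 to 0.15 × 100 = 15 ng/ml.

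**Step 4. Men to whom the threshold is relevant.** Expected MRI-negative men in round one: 871 − 521 = 350, which is 350/871 = 40% of those referred and 350/11,167 = 3.1% of participants. This is an upper bound on the men the density rule could send to biopsy. The plan does not say how many would exceed the threshold, and I do not estimate it.

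**The case against.** **The unit may be a reading error.** It occurs once, as a formula recovered from PDF by a program, and such text can be misread. That stands, and it is why the source file should be checked first. It is also true that 0.15 itself cannot be verified, because the publication cited for it is not available here. Only the scale, ng/ml², follows from the documents.

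**Nobody would apply the printed threshold.** This also largely stands. The slip reveals itself, and the stated purpose excludes a rule that selects no one. A reader might infer that high-density MRI-negative men will in fact go unbiopsied. The documents do not support that: they show a faulty unit, not faulty conduct. Men with PSA at or above 3 are in any case re-invited after two years.

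**The denominator is not certain.** The plan does not restrict the 290 to MRI-positive men. It allows biopsy of high-density MRI-negative men and, for a random sample of men with a negative panel or MRI, says that those with a "negative MRI will also undergo systematic biopsy for assessment of diagnostic accuracy". Men who cannot have MRI receive ultrasound instead. Relabelling the 55% as the yield among MRI-positive men assumes that none of the 290 come from these groups. That objection stands and shapes the fix.

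**A tempting further claim.** Screening protocol states: "These men will be referred to MRI and only MRI-positive men will be biopsied". A reader might infer that this contradicts the biopsies of MRI-negative men under Diagnostic procedures. It does not amount to a conflict. Screening protocol presents itself as a brief account, and the next section sets out the exceptions explicitly, so a reader following the plan reaches a clear biopsy rule. A cross-reference would be a drafting preference only.

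**Conclusion.** Two low-priority corrections hold.

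1. As printed, the density threshold is 1,000 times the scale implied by PSA in ng/ml and volume in ml, and read literally it would select essentially none of about 350 expected MRI-negative men. This assumes that the printed unit is what the source file shows. That 0.15 is the intended number is likely but for the sponsor to confirm.
2. The 55% does not belong to the men referred for MRI, for whom the ratio is 33%. It matches the MRI-positive men (55.7%), which is the likeliest intended denominator but not an established one. The 290 and the 2.6% agree with each other and can stay.

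Neither point reaches the power calculation, which in section 6 rests on population mortality rates and does not use this yield. Sample size and the primary mortality analysis are likewise unaffected.

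**What to change.** - **Threshold:** check the unit against the source file, have the sponsor confirm the value, and print it as 0.15 ng/ml² (equivalently 0.15 µg/l per ml). Check that any working procedure or case report form derived from this sentence carries the same unit.
- **Yield:** restate the 290 as 33% of men referred to MRI. This keeps the plan's denominator and does not require every case to come from an MRI-positive man. Alternatively, restate it as 55% of MRI-positive men, provided the sponsor confirms that the 290 exclude cancers found in MRI-negative or ultrasound-only men.

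The cost is one unit and one percentage or label, with no change to design or analysis.

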#### Data collection

Cost data will also be collected for economic analyses, including procedure codes, DRG group and actual billing information for each hospital visit (including outpatient visits) from the hospital database.

Questionnaire surveys will be used for random samples of men in both arms to obtain utility estimates (with the 15D instrument) and information on out of pocket health care costs. For indirect costs, data on sickness benefits will be obtained from the Social Insurance Institution (SII) database (the governmental agency providing all benefits through the national comprehensive health insurance system).

Adverse effects of biopsy are evaluated, with questionnaire surveys of complications, including assessment of bleeding, lower urinary tract symptoms (LUTS) and erectile dysfunction (ED) at four weeks (with baseline data on LUTS and ED prior to biopsy collected at the time of the examination), as well as hospitalisation data on septic infections. The questionnaire instruments used are ICIQ-MLUTS for LUTS and IIEF-5 for ED; in addition, data on antibiotic prescriptions following biopsy will be obtained from the SII nationwide prescription database.

Information on prostate cancer cases diagnosed in the entire study population will be obtained from the Finnish Cancer Registry (with >99% coverage of cancer cases in Finland), so that interval cancers as well those in non-participants and the control arm can be identified and intention to screen analyses of prostate cancer incidence in the entire study population conducted. Detailed clinical information on Gleason score, PSA at diagnosis, treatment and other features will be retrieved from the electronic medical record using the ECRF software customised for the trial.

As for patient-oriented outcomes, assessment of the generic quality of life (SF12 and 15D) will be conducted for a sample of men at each stage of the screening process. The validated Extended Prostate Cancer Index Composite (EPIC) questionnaire is used for monitoring quality of life and adverse effects of treatment in all men within trial diagnosed with prostate cancer (regardless of arm, hospital and treatment).

Follow-up for vital status and emigration is through Population Registry, and causes of death will be obtained from Statistics Finland. We have previously shown excellent agreement between the official causes of death and a blinded cause of death adjudication panel (kappa 0.9, Mäkinen 2008, Kilpeläinen 2016) and no adjudication committee will be used, because of the demonstrated validity of the Statistics Finland cause of death data.

## 5. TRIAL SCHEDULE

The study will commence in 2018, with randomisation of half of the men during the first year. The first screening round will be completed in 2019. A summary of the timeline is shown in Table 1.

Table 1. Planned schedule of the trial conduct

	Trial years 1-2	Years 3-4	Years 5-6	Years 7-8	Years 9-10
All subjects	Recruitment				
All participants	1 st screening				
Men with PSA>3		2 nd screen	3 rd screen	4 th screen	5 th screen
Men with PSA 1.5-3			2 nd screen		3 rd screen
Men with PSA<1.5				2 nd screen	

## 6. POWER CALCULATIONS & STATISTICAL ANALYSIS PLAN

The main outcome of the trial is prostate cancer mortality. An intention to screen analysis will be performed, with all men in the groups defined by random allocation, regardless of compliance. This is the gold standard for randomised trials, as it gives an unbiased effectiveness estimate, which is realistic for application (though lower and 'diluted' compared with an efficacy estimate based on compliers only). The only post-randomisation exclusions will be based on prostate cancer diagnosis prior to entry, as inevitably some recent cases will be found out only after randomisation. Follow-up starts at randomisation, and ends at death. Dates of death are registered also for men who have emigrated, but in case of a missing cause of death, the event will be censored. Cox regression will be used with prostate cancer death as the outcome. Randomisation is expected to result in balanced distribution of age, with no need for adjustment.

Based on the most recent age-specific population rates (2010-2014) and the age structure of the male population, the expected number of prostate cancer deaths in the control arm is 222 at 10 years, with sufficient statistical power ( $1-\beta=0.8$ ,  $\alpha=0.05$  two-sided) to detect a 33% reduction (hazard ratio,  $HR\leq 0.67$  for the screening arm, cumulative mortality 29 vs. 44 per 10,000 men) in prostate cancer mortality. This is calculated considering the overall mortality from other causes (ranging from 7 per 100,000 at age 55 to 210 per 100,000 at age 75), yielding a total of 475,000 person-years of follow-up. At 15 years of follow-up, the expected number of deaths in the control arm is 451, with a minimal detectable effect size of 26% ( $HR\leq 0.74$ , 67 vs. 90 deaths per 10,000 men, based 912,800 person-years of follow-up).

A secondary analysis of prostate cancer mortality will be performed using the Cuzick method to correct for non-compliance and contamination (Cuzick 1997, Roobol 2009, Kilpeläinen 2015).

Intermediate outcomes include cumulative incidence of advanced (T3-T4 or M1) prostate cancer (number of cases relative to population size, not using incidence density to avoid the lead-time bias due to early

detection by screening), and cumulative incidence of low-risk cancer (Gleason<7) as an indicator of overdiagnosis.

Analysis of screening test performance, including sensitivity and specificity, positive and negative predictive value will be conducted, assessing also the accuracy of 4Kscore and MRI. Interval cancer incidence will be analysed as an indicator of program sensitivity, besides participation and its determinants. Cancer detection and screening test performance will also be evaluated by major risk factors including family history, genetic risk and major lifestyle determinants.

Short-term quality of life impact of screening will be evaluated among screening participants, and adverse effects of prostate biopsy analysed as outlined above. Quality of life and psychosocial impacts among men diagnosed with prostate will be assessed using the EPIC instrument and the Memorial Anxiety Scale for Prostate Cancer (MAX-PC), enrolling screen-detected and interval cases, as well as those diagnosed among non-participants and in the control arm. Follow-up will be carried out at diagnosis and 6, 12 and 48 months after it. A mobile phone app is used to collect data on patient-oriented outcomes.

Economic evaluation will commence with cost analysis, and the final analysis of incremental cost effectiveness ratio (with a decision analysis) can be conducted only once data on both long-term cost and real outcome data on both utilities (quality-adjusted life-years) and mortality are available. However, early assessment can give some predictions about potential effects size required for the intervention to be regarded as cost-effective.

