### 3. TARGET POPULATION

We will identify all 67,000 men aged 50-63 years and residing in Tampere or Helsinki from the Population registry, and after exclusion of men with a prior diagnosis of prostate cancer (expected number 200), randomize them into two trial arms in ratio 1:3 (16,750 men allocated to the screening arm expected). Randomization is based on computer-generated random numbers and will be conducted in five batches annually (10% of the entire population at a time). This procedure is chosen in order to include only men alive and free of prostate cancer (with up-to-date information on cancer and vital status). Men with a permanent address abroad are not eligible.

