are performed at five and eight years in accordance with sequential analysis rules (total alpha spending 0.005 of the two interim analyses according O'Brien-Fleming).

The study question satisfies equipoise criteria, i.e. balance of uncertainty (superiority of the evaluated intervention versus standard practice is not established). All procedures applied represent viable clinical options meeting current standards of care. The two screening tests based on a blood sample constitute the only experimental procedure performed solely for research purposes. Hence, the allocation based on randomisation is the only deviation from the normal health care and patient management. Screen-positive men are referred to diagnostic examinations just as any other patients, and undergo the procedures similar to other patients. This means that the results are readily applicable to public health policy. The generalisability is further enhanced by the Zelen-type randomisation, with consent sought only from the men in the intervention arm after randomisation. This ensures ethical conduct of research, as nobody is denied access to proper health care by the randomisation.

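### The stated 80% power at 10 years for HR 0.67 is slightly optimistic (about 75–77% by simulation), and no single method tried gives both the 10-year and 15-year detectable effects

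*Combined protocol and SAP*

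**What the plan says.** Section 3 (Target Population) gives the base: "We will identify all 67,000 men aged 50-63 years and residing in Tampere or Helsinki", randomised 1:3 with 16,750 expected in the screening arm, which leaves 50,250 controls.

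Section 6 (Power Calculations & Statistical Analysis Plan) names prostate cancer mortality as the main outcome and Cox regression by intention to screen as the analysis. For 10 years it says that "the expected number of prostate cancer deaths in the control arm is 222 at 10 years, with sufficient statistical power". It claims power 0.8 at two-sided alpha 0.05 for a 33% reduction, HR 0.67 or lower, which it expresses as "cumulative mortality 29 vs. 44 per 10,000 men". For 15 years it expects 451 control deaths "with a minimal detectable effect size of 26" per cent (HR 0.74 or lower). It does not name the formula or software behind either figure.

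**The concern.** With three controls per screened man and the lower hazard in the smaller arm, few of the deaths fall in the screening arm. A formula that fixes the split of deaths at the allocation ratio then understates the variance of the log hazard ratio and overstates power. The stated 10-year power looked too high for this reason, and the 10- and 15-year effects did not look as if they came from the same calculation.

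The stake is modest. Ten years is the earliest horizon for which the plan states a power. If the chance of missing a true 33% reduction is nearer 23–25% than 20%, readers should know that when they interpret a 10-year result that is not significant.

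**Working it through.** **Inputs.** Control deaths are 222 at 10 years and 451 at 15 years, HRs are 0.67 and 0.74, alpha is 0.05 two-sided and power is 0.80 (all Section 6). Arms are 50,250 and 16,750 men (Section 3). Removing the 200 expected exclusions leaves power at 10 years unchanged to three decimals.

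**Expected deaths at 10 years.** Screening arm: 222/3 × 0.67 = 49.6. Total: 271.6. Screening share: 49.6/271.6 = 18.3%, against 25% of men.

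**Reproducing the stated 80%.**
- Schoenfeld: power = Φ(|ln HR| × √(D × 0.25 × 0.75) − 1.960) = Φ(0.4005 × √(271.6 × 0.1875) − 1.960) = Φ(2.858 − 1.960) = 81.5%. Required deaths for 80% are 262, against 271.6 expected.
- Unpooled difference in proportions: rates are 44.18 and 29.60 per 10,000, the difference is 0.001458 and its standard error is 0.0005135. Power = Φ(2.839 − 1.960) = 81.0%.

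Both support the 10-year line.

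**Using the expected deaths in each arm.** Schoenfeld's variance for the log HR is 1/(271.6 × 0.1875) = 0.0196. The variance from the expected deaths is 1/222 + 1/49.6 = 0.0247, about a quarter larger. The Wald formula with that variance gives Φ(0.4005/0.1571 − 1.960) = 72.2%. The pooled two-proportion formula has null standard error 0.0005669, so power = Φ((0.001458 − 1.960 × 0.0005669)/0.0005135) = 75.0%. Freedman's formula for 1:3 allocation gives 72.8% and the arcsine formula 77.3%.

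**Simulation.** The formulas range from 72% to 81.5%, so the comparison was simulated: Poisson deaths with mean 222 in the control arm and 74 × HR in the screening arm, two-sided 0.05, 400,000 trials per HR (1,000,000 for HR 2/3).

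| HR | Score | Wald | Likelihood ratio |
|---|---|---|---|
| 0.67 | 75.4% | 75.1% | 76.9% |
| 2/3 | 76.3% | 76.0% | 77.8% |
| 0.66 | 78.2% | 78.0% | 79.6% |
| 0.65 | 80.8% | 80.6% | 82.1% |

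Power reaches 80% at HR 0.653 for the score test and just below 0.66 for the likelihood-ratio test, a reduction of about 34–35%.

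**Both horizons together.** At 15 years and HR 0.74 the screening arm expects 451/3 × 0.74 = 111.2 deaths. Simulated power is 83.5% (score), 83.4% (Wald) and 84.3% (likelihood ratio), so the stated 26% has more than 80% power. The HR giving 80% power under each method is:

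| Method | 10 years | 15 years |
|---|---|---|
| Stated in Section 6 | 0.67 | 0.74 |
| Schoenfeld | 0.675 | 0.762 |
| Unpooled proportions | 0.674 | 0.762 |
| Arcsine | 0.660 | 0.754 |
| Pooled proportions | 0.652 | 0.751 |
| Freedman | 0.641 | 0.745 |
| Log-HR Wald | 0.638 | 0.744 |
| Simulation (score) | 0.653 | 0.750 |

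The two methods that support the 10-year figure give about 24% at 15 years. The two that give 26% at 15 years give about 36% at 10 years.

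**The case against.** The strongest reply is that nothing was miscalculated. Schoenfeld is the usual formula for a Cox analysis and returns 81.5%, and the unpooled difference in proportions independently returns 81.0%. That stands. A reader might infer that the 80% is an arithmetic error, or that it survives under one formula only. Neither is true.

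The size of the gap also depends on rounding and on the test. With an HR of 2/3 and a likelihood-ratio test, which the plan does not rule out, simulated power is 77.8%, so the shortfall is about 2 points rather than 5. This stands too, and is why a range is given.

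Two further inferences are tempting and not supported. One is that 29 against 44 per 10,000 contradicts HR 0.67. In fact 44.18 × 2/3 = 29.45, which prints as 29, while 2/3 prints as 0.67 and as a 33% reduction. The other is that the interim looks in Section 7, with "total alpha spending 0.005 of the two interim analyses", leave a final alpha of 0.045. The plan gives no final level, and plain subtraction ignores the correlation between looks.

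Finally, a non-significant result would be read from its confidence interval, and Section 8 (Risks) already acknowledges larger threats, including a possible true effect near 16%. That limits the importance of this point. It does not explain why the two stated effects fit no common method.

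**Conclusion.** The concern holds as a minor correction. At 222 control deaths and 1:3 allocation, power for a 33% reduction is about 75–77% (76–78% if the unrounded HR is 2/3) rather than 80%. The effect detectable with 80% power at 10 years is about 34–35%. The 15-year figure errs slightly the other way, with about 25% detectable against 26% stated. None of the seven methods compared, simulation included, yields both stated HRs.

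This rests on the plan's own expected deaths, a proportional effect, full alpha of 0.05 at the analysis, and Poisson counts as a stand-in for the Cox comparison, which is reasonable for an event affecting under 1% of men. It does not show that the trial is too small or that the design must change.

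**What to change.** In Section 6, name the power method and use the same one at both horizons. It should use the expected deaths in each arm, or be a simulation of the planned test. Restate the 10-year line as about 75–77% power for a 33% reduction, or 80% power for a reduction of about 35%. Restate the 15-year line as 80% power for a reduction of about 25% (HR 0.75). Say which Cox test is assumed and give the HR to three decimals, so that the figures can be reproduced.

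The cost is the rewording of one paragraph. The 10-year statement becomes slightly less favourable and the 15-year one slightly more so. No more men are needed.
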